Population (mention key inclusion-exclusion criteria):	
• Age ≥ 18 years• Postmenopausal women with ER-positive, HER2-negative locally advanced or metastatic breast cancer who receive treatment without curative intent
○ The line of therapy for patients in EDB1 and EDB3 is implicitly advanced/metastatic because the line of therapy classification starts after their advanced/metastatic diagnosis in the respective database○ In EDB4, patients must explicitly have any evidence of a metastasis prior initiating palbociclib plus letrozole or letrozole alone• Adenocarcinoma histology
• No prior systemic treatment for advanced/metastatic disease• ECOG 0 or 1
Exposure:	Initiation of palbociclib plus letrozole
Comparator:	Initiation of letrozole
Outcome:	Primary: Time to all-cause mortality (OS) Secondary: Time to next treatment (TTNT)
Time (when follow up begins and ends):	From the day of treatment initiation until outcome. Death, last observed clinical activity/last sign of the patient being alive, or data cut-off, whichever occurred earliest
Setting:	1L ER-positive, HER2-negative locally advanced or metastatic adenocarcinoma of the breast
Main measure of effect:	Hazard ratio (95% CI)

The emulation of the main protocol elements of the PALOMA-2 is illustrated side by side in **Table 2**.

Table 2. Trial emulation table summarizing the main protocol elements of the PALOMA-2 trial and the planned emulation.

Protocol component	PALOMA-2 RCT	Emulation	Comments

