- This is a safety criterion for the trial and less relevant to real-world treatment setting, given that patients received treatments of interest

- 2015 was the approval year for palbociclib, and 2022 is when the final OS results of the competitor ribociclib were published⁷

Treatment strategies	Palbociclib + letrozole vs. placebo + letrozole	Patients initiating palbociclib + letrozole vs. letrozole alone, using an exposure assessment window to capture combination treatments, based on each data vendor's proprietary business rules	Use treatment start dates to define exposure
Assignment procedures	Randomized 2:1 to palbociclib + letrozole or placebo + letrozole	Propensity score-based matching or weighting to emulate randomization	Balance baseline covariates to reduce confounding
Follow-up period	Time from randomization to death or censoring	Time from treatment initiation to death or censoring	
Outcome	Primary: Progression-free survival (PFS) per investigator assessment Secondary: Overall survival (OS)	Primary: OS Secondary: Time-To-Next-Treatment (TTNT)	Lack of good measurement of progression, so inferred by initiation of next treatment as a secondary endpoint rather than primary
Causal contrast	Intent-to-treat effect	Effect of initiating palbociclib + letrozole versus letrozole	Analogous to ITT; emulates initiation rather than adherence

*Includes the following: apelisib, capecitabine, carboplatin, cisplatin, cyclophosphamide, docetaxel, doxorubicin, epirubicin, eribulin, exemestane, fluorouracil, gemcitabine, goserelin, ixabepilone, methotrexate, olaparib, paclitaxel, tamoxifen, talazoparib, toremifene, and vinorelbine.

6. Research methods

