6.6. Setting

6.6.1. Context and rationale for definition of time 0 (and other primary time anchors) for entry to the study population

Time 0 in this database study is defined as the date a patient initiated palbociclib plus letrozole (exposure) or letrozole alone (comparator) as part of their 1L systemic antineoplastic treatment for advanced/metastatic adenocarcinoma of the breast. This aims to emulate the date of randomization and cohort entry in the RCT (the time from randomization to first dose is not reported in the [clinicaltrials.gov study report](https://clinicaltrials.gov/study/NCT02420417) or the trial articles).

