6.6.4. Context and rationale for exposure(s) of interest

The exposure and comparator were defined to emulate the agents compared for the trial, i.e., initiation of palbociclib plus letrozole versus letrozole alone in a 1L metastatic setting.

- **EDB1:** Exposure is derived using a manually curated line of therapy (LOT) table provided by the data partner that programmatically categorizes treatment regimens into a coherent line of treatment, based on a proprietary business rule with an exposure assessment window. That is, each patient is represented with one row per curated line of therapy with corresponding information on line number, regimens as well start and end dates. Based on this table, patients are identified who received palbociclib-plus-letrozole or letrozole-alone treatment regimen by their generic names (string match) in 1L, using the exposure assessment window; follow-up begins after the end of the exposure assessment window. The LOT implicitly only considers regimens that were given as part of a metastatic disease setting. Importantly, the LOT table applies a proprietary business rule to determine line of therapy, which includes an exposure assessment window relative to advanced cancer diagnosis. More details and annotated code to identify initiators can be found in the 'Derive cohort EDB1' Quarto report (access within MGB network only).
- **EDB3:** Exposure is derived using a manually curated line of therapy (LOT) table provided by the data partner that programmatically categorizes treatment regimens into a coherent line of therapy, based on a proprietary business rule with an exposure assessment window. That is, each patient is represented with one row per curated line of therapy AND drug name with corresponding information online number, regimens as well start and end dates. Based on this table, patients are identified who received only palbociclib and letrozole within the first line of therapy, and letrozole alone within the first line of therapy by their generic names (string match), using the exposure assessment window; follow-up begins after the end of the exposure assessment window. The LOT implicitly only considers regimens that were given as part of a metastatic disease setting. More details and annotated code to identify initiators can be found in the 'Derive cohort EDB3' Quarto report' (access within MGB network only).
- **EDB4:** For the EDB4 database, the following logic is applied.

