 - Identify patients with evidence of a metastasis from the diagnosis table in which the earliest date associated with evidence of metastasis is captured as a structured field (metastasis date).
 - Identify all potential antineoplastic drugs typically used in advanced/metastatic breast cancer (see list below*). Only these are considered.
 - Identify patients who received any of the PALOMA-2 drugs as the first antineoplastic treatment on or after the metastasis date.
 - Identify and exclude patients who received palbociclib before the metastasis date.
 - Follow-up begins after the end of the exposure assessment window.

***Antineoplastic drugs considered:** abemaciclib, alpelisib, anastrozole, atezolizumab, bevacizumab, capecitabine, carboplatin, cisplatin, cyclophosphamide, docetaxel, doxorubicin, entrectinib, epirubicin, eribulin, etoposide, everolimus, exemestane, fluorouracil, fulvestrant, gemcitabine, goserelin, ixabepilone, larotrectinib, letrozole, methotrexate, nab-paclitaxel, olaparib, paclitaxel, palbociclib, pembrolizumab, pertuzumab, ribociclib, sacituzumab govitecan-hziy, talazoparib, tamoxifen, toremifene, trastuzumab, trastuzumab-deruxtecan, vinorelbine.

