6.6.5. Context and rationale for outcome(s) of interest

The primary outcome for the database study was defined to emulate the primary outcome for the trial, time from index to death due to any reason (OS).

Operational definitions:

- **EDB1:** Time in [days, months and years] from index date to death due to any reason. The date of death is de-identified to month-level granularity or (rarely) to year-level granularity and the date of death is therefore imputed to the 15th of a month or mid-year/July 2 of the year of death, respectively. In If there is no indication that a patient died during the study period, the patient is censored. The censoring date is defined as the last visit or treatment encounter or data cut-off date, whichever occurred earlier. The OS endpoint is operationalized using a parameterized R function *edb1_get_os()* and more details can be found in the attached pdf documentation.
- **EDB3:** Time in [days, months and years] from index date to death due to any reason. The date of death is de-identified to month-level granularity and the day of death is therefore imputed to the 15th of a month. Patients without evidence of death are censored at the earlier of the last recorded activity date or the data cut-off date. Activity dates are defined as documented in Table 4. Death dates are compiled from Electronic Medical Records (EMR), manual curation, and third-party death data, linked via de-identified tokens generated from hashed personally identifiable information (PII). Sources of death dates are prioritized as follows: (1) manual curation, (2) EMR, and (3) third-party sources. For privacy reasons, the final reported death date is shifted to the nearest Sunday within four days of the actual date. Manually curated death dates follow a prioritization hierarchy of source documentation: death certificate first, followed by scanned obituaries or death announcements, and lastly exact dates reported by providers without other supporting documentation. The OS endpoint calculation uses a parameterized R function (*edb3_get_os()*), with detailed documentation provided in the attached PDF.

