6.6.7. Context and rationale for covariates

We identified a series of covariates that are strong prognostic factors for the outcome and auxiliary covariates which may be useful to impute missing data. Such covariates comprise demographics, covariates indicating disease-severity, cancer-specific covariates as well as pathological and genetic factors. In addition, selected labs and vitals are considered since they were shown to carry a high amount of prognostic information as described in Becker, Weberpals, et al.¹¹ For these variables, additional plausibility checks and transformations are carried out. In detail, labs and vitals are individually checked if they cross a certain biologically implausible threshold (e.g., a heart rate of 0) in which cases the values are set missing and imputed in a next step. These thresholds were compiled by experienced practicing physicians and medical oncologists and are listed in appendix **Table 8** and **Table 9**.

Note that not all covariates are available across all databases used for this trial emulation. In the analytical stage, the most comprehensive model will be fit for each database individually.

Table 5. Operational definitions of key covariates used for trial emulation.

Characteristic	Harmonized analysis variable name	R function to derive covariate (see pdf in appendix)	Details ¹	Variable encoding	Assessment window
Age at index date	dem_age_index	edbx_get_demographics()	Age measured at index date	Binary (<60, 65+); modelled continuously in ROPRO ¹⁰	[0;0]
Year of index date	c_year_index	De novo derived from dt_index	Calendar year in which patient initiated study treatment	Nominal (<2020, 2020+)	[0;0]
Family history	dem_family_history	edbx_get_demographics()	Family history of cancer. Not available in EDB1.	Logical (TRUE, FALSE)	[0;0] (no specific date is associated)
Race	dem_race	edbx_get_demographics()	Race categorized as in the original RCT	Binary (Asian vs non-Asian)	[0;0]
Ethnicity	dem_ethnicity	edbx_get_demographics()	Ethnicity	Hispanic, Non-Hispanic	[0;0]
Region	dem_region	edbx_get_demographics()	US region patient receives care in; if given on a state level, region is manually mapped (see Table 10)	Nominal (Northeast, South, West, Midwest)	[0;0]
Practice type	dem_practice	edbx_get_demographics()	Setting patient is receiving care at. Not available in EDB3 and EDB4.	Nominal (academic, community, academic & community)	[-inf;0]

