Socio-economic status	dem_ses	edbx_get_demographics()	Socioeconomic status (SES) index based on residence area of patient. Not available in EDB3 and EDB4.	Nominal (from '1 - Lowest SES' through '5 - Highest SES')	[-inf;0]
Smoking	c_smoking_history	edbx_get_demographics()	History of current or former (= TRUE) or never (= FALSE) smoking on or anytime before index date; if there are multiple records per patient, any evidence of former/current smoking is prioritized. IN EDB1, "smoking history" is not available for breast cancer.	Binary logical (TRUE, FALSE)	[-inf;0]
ECOG	c_ecog	edbx_get_ecog()	ECOG performance status measured closest to index date within assessment window. In	Nominal (0, 1, 2, 3, 4); modelled as ordinal numeric in ROPRO ¹⁰ ; due to I/E	[-90;0]

Characteristic	Harmonized analysis variable name	R function to derive covariate (see pdf in appendix)	Details ¹	Variable encoding	Assessment window
			case of ties, the lower ECOG value is selected	criteria ECOG is modelled as a binary (0, 1) covariate	
Stage	c_stage_initial_dx	edbx_get_diagnosis_solid()	AJCC summary group stage at initial diagnosis	Ordinal numeric (from 0 to IV with sub-categories, e.g., IA1) ¹⁰	[-inf;0] at initial diagnosis of primary cancer
De novo metastatic status	c_de_novo_mets_dx	edbx_get_diagnosis_solid()	Evidence of presence of one or multiple metastases at/before initial diagnosis	Binary logical (TRUE, FALSE)	[-inf;0] at initial diagnosis of primary cancer
Number of metastatic sites	c_number_met_sites	edbx_get_diagnosis_solid()/edbx_get_number_met_sites_solid()	Number of metastatic sites for a given patient before/on index date	Integer	[-inf;X]; Proprietary business-rule-based covariate assessment window
Time between initial diagnosis to index date	c_time_dx_to_index	edbx_get_diagnosis_solid()	Time in days between initial diagnosis to index date. Quartiles will be used because there may be “negative” times intervals due to date imprecision of the lines of therapy.	Categorical (quartiles)	[-initial dx;0]
Time between earliest evidence of a metastatic and index date	c_time_met_dx_to_index_quartiles	edbx_get_diagnosis_solid()	Time in days between earliest evidence of a metastatic diagnosis and index date. Quartiles will be used because there may be “negative” times intervals due to date imprecision of the lines of therapy.	Categorical (quartiles)	[met dx;0]

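### Follow-up starts at treatment initiation in some sections and after the exposure assessment window in another; unreconciled, the OS clock can carry immortal time that favours palbociclib

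*Combined protocol and SAP*

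**What the plan says.** Two starting points are given for the same clock.

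**Treatment initiation.** Table 1 (section 5) runs follow-up as "From the day of treatment initiation until outcome". The emulation column of Table 2 has "Time from treatment initiation to death or censoring". Section 6.6.1 agrees ("Time 0 in this database study is defined as the date a patient initiated palbociclib plus letrozole (exposure) or letrozole alone (comparator"). For each database, section 6.6.5 defines OS as "Time in [days, months and years] from index date to death due to any reason". Table 5 derives the index year from the index date and describes it as "Calendar year in which patient initiated study treatment", so the index date is the initiation date.

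**End of the window.** Section 6.6.4 states for EDB1 and EDB3 that "follow-up begins after the end of the exposure assessment window", and for EDB4 "Follow-up begins after the end of the exposure assessment window".

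Table 2 gives the window's purpose: to recognise combination treatment under each vendor's rules. Its length is withheld as proprietary. For EDB1, section 6.6.4 describes it in relation to the advanced diagnosis.

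Table 5 has a related mismatch. The metastatic-site count is "Number of metastatic sites for a given patient before/on index date", but its assessment window is [-inf;X], with X set by the vendor rule.

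**The concern.** This is the clock of the primary endpoint in both primary databases. One programmer working from section 6.6.4 and another from section 6.6.5 would build different OS datasets.

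The choice can move the estimate. The window exists because the second drug may be recorded after the first. If survival time counts from initiation but the arm is settled later, a patient who starts letrozole, is due to add palbociclib and dies first is counted as letrozole alone. That early death moves from the exposed arm to the comparator. Matching on baseline covariates cannot undo this, because the error comes from events after baseline.

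The window-end clock has its own gap. A death inside the window then gives negative follow-up. The only rule for such times (section 6.7.1) excludes them and attributes them to imputed death dates, so real in-window deaths could be dropped without being counted by arm.

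Immortal time is raised only for left truncation in EDB4, and none of the 12 sensitivity analyses in Table 8 varies the start of follow-up.

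**Working it through.** **1. The plan's own figures.** The plan gives no number for the window, so the available check is the power in section 10.3. Schoenfeld, two-sided alpha 0.05, 50% exposed, HR 0.92: power = Φ(√(d/4)·|ln 0.92| − 1.960).
- EDB1, d = 1021: Φ(1.332 − 1.960) = 0.265 (stated 0.27).
- EDB3, d = 331: Φ(0.758 − 1.960) = 0.115 (stated 0.11).

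Both reproduce. The point does not depend on power, but the event counts are used in step 5.

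**2. Do the texts allow one reading?** A landmark analysis, delayed entry at the window end, or an index date redefined as the window end would each reconcile the sections. None is stated.

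**3. Deaths inside the window.** Inputs: control median OS 51.2 months (section 4); matched sets of 1812 and 610 (section 10.3), that is 906 and 305 per arm. Assumptions: constant hazard and windows of 28, 60 or 90 days. P = 1 − 2^(−w/51.2), with w in months of 30.4375 days.

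| Window | P(death in window) | EDB1, of 906 per arm | EDB3, of 305 per arm |
|---|---|---|---|
| 28 days | 0.0124 | 11 | 4 |
| 60 days | 0.0263 | 24 | 8 |
| 90 days | 0.0392 | 36 | 12 |

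**4. Effect on the HR if the clock runs from initiation.** Assume a share f of combination patients starts palbociclib uniformly over the window, after letrozole. Cohorts of 1,000,000 were simulated per scenario with true HR 1.00 and censoring at 60 months. Anyone dying before palbociclib was classed as letrozole alone. The multiplier on the Cox HR, at constant hazard:

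| Window | f = 25% | f = 50% | f = 100% |
|---|---|---|---|
| 28 days | 0.995 | 0.989 | 0.978 |
| 60 days | 0.989 | 0.978 | 0.954 |
| 90 days | 0.982 | 0.965 | 0.932 |

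A hand check agrees. The share of combination patients moved is m ≈ f·P/2, and the 60-month death probability is D = 1 − 2^(−60/51.2) = 0.556. Moving m deaths from one arm to the other gives a ratio of about (D − m)/(D + m).
- 28 days, f = 25%: m = 0.00155, ratio 0.994.
- 90 days, f = 100%: m = 0.0196, ratio 0.932.

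With the hazard doubled in the first three months, the simulated range is 0.990 down to 0.876. With the clock started at the window end among survivors, the multiplier is about 1.00 throughout.

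**5. Scale.** Pooled events are 1021 + 331 = 1352, so the SE of the log HR is about 2/√1352 = 0.054. At constant hazard the shift runs from |ln 0.995|/0.054 ≈ 0.1 SE to |ln 0.932|/0.054 ≈ 1.3 SE. A true HR of 0.96 would appear as about 0.955 (0.96 × 0.995) down to 0.895 (0.96 × 0.932).

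**The case against.** Section 6.6.4 is the operational exposure section and already gives a post-window start for all three databases. On that reading the clock carries no immortal time, and what remains is to align the text and state the rule for in-window events. This stands as far as it goes, but it does not settle which section the OS functions follow.

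Several stronger readings are tempting, and the documents do not support them.
- *The plan is biased towards palbociclib.* Only one branch produces that. The bias is absent if both drugs start together. It is also absent if time 0 is the start of the second drug, and section 6.6.1 can be read that way, since it dates time 0 by initiation of the combination. How often palbociclib starts late is not shown.
- *The window opens at the start of the line of therapy.* No section says so, and the EDB1 text points to the advanced diagnosis. A window anchored there could end before treatment starts. Sensitivity analysis #10 expects some patients with more than a year between metastasis and index.
- *Dropping in-window deaths while counting from initiation distorts the comparison.* If the window has the same length from initiation for everyone, every survival time gains the same constant. The Cox HR depends only on the order of events, and the shift cancels in the median difference. Each arm's own median would be overstated.
- *The metastatic-site count should be cut at index.* The [-inf;X] window was added deliberately in V1.2, and Table 5 acknowledges imprecise dates around line start. A hard cut could discard baseline metastases dated slightly late.

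Figure 1, the OS function documentation and the cohort derivation reports are not available here, and V1.2 revised Figure 1 for this window. They may fix the order of events, but the conflicting text would still need correcting.

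**Conclusion.** The contradiction is certain. It concerns the primary endpoint's time origin in EDB1 and EDB3, and must be resolved before the OS analysis is run. Immortal time is a conditional consequence: it needs the initiation clock, an arm read from later records, and some palbociclib starts after time 0. Where it occurs, it favours palbociclib.

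At constant hazard the multiplier of about 0.995 to 0.93 rests on assumed window lengths and late-start shares, neither of which the documents give. At the low end it is negligible. At the high end it exceeds the distance between the trial's 0.96 and no effect, which matters in a study designed to judge concordance with a near-null result.

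**What to change.** - Use one time origin for OS and TTNT in both arms and all databases: the day after the exposure assessment window ends, and never before the start of the first-line regimen.
- Require patients to be alive and uncensored on that day. Report in-window deaths and censoring by arm and database, separately from exclusions caused by imputed death dates.
- State for each database whether the window is anchored on line start or on advanced diagnosis. Its length can stay undisclosed, provided a window-end date per patient can be derived or supplied; section 6.6.4 mentions only line start and end dates, so this needs checking with the vendors.
- Align Table 1, Table 2, section 6.6.1, section 6.6.5 and the OS functions with this rule.
- Run the initiation clock as a sensitivity analysis.
- Keep baseline covariates anchored at treatment start. For the metastatic-site count, reconcile the description with the [-inf;X] window without imposing a cut at index.

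Cost: the text changes are small. The estimate becomes conditional on surviving the window, and a few in-window deaths are lost (about 11 to 36 per arm in EDB1 under the assumptions above). If the current code uses the initiation clock, the cohort changes, so imputation, matching and the attrition, balance and event counts in sections 10.1 to 10.3 must be rerun.

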6.6.5. Context and rationale for outcome(s) of interest

The primary outcome for the database study was defined to emulate the primary outcome for the trial, time from index to death due to any reason (OS).

Operational definitions:

- **EDB1:** Time in [days, months and years] from index date to death due to any reason. The date of death is de-identified to month-level granularity or (rarely) to year-level granularity and the date of death is therefore imputed to the 15th of a month or mid-year/July 2 of the year of death, respectively. In If there is no indication that a patient died during the study period, the patient is censored. The censoring date is defined as the last visit or treatment encounter or data cut-off date, whichever occurred earlier. The OS endpoint is operationalized using a parameterized R function *edb1_get_os()* and more details can be found in the attached pdf documentation.
- **EDB3:** Time in [days, months and years] from index date to death due to any reason. The date of death is de-identified to month-level granularity and the day of death is therefore imputed to the 15th of a month. Patients without evidence of death are censored at the earlier of the last recorded activity date or the data cut-off date. Activity dates are defined as documented in Table 4. Death dates are compiled from Electronic Medical Records (EMR), manual curation, and third-party death data, linked via de-identified tokens generated from hashed personally identifiable information (PII). Sources of death dates are prioritized as follows: (1) manual curation, (2) EMR, and (3) third-party sources. For privacy reasons, the final reported death date is shifted to the nearest Sunday within four days of the actual date. Manually curated death dates follow a prioritization hierarchy of source documentation: death certificate first, followed by scanned obituaries or death announcements, and lastly exact dates reported by providers without other supporting documentation. The OS endpoint calculation uses a parameterized R function (*edb3_get_os()*), with detailed documentation provided in the attached PDF.
- **EDB4:** Time in [days, months and years] from index date to death due to any reason. The date of death is de-identified to month-level granularity and the day of death is therefore imputed to the 15th of a month. If there is no indication that a patient died during the study period, the patient is censored. The censoring date is defined as the last date of vital signs recorded as proof that the patient was alive at that time (de-identified to week-level granularity) or data cut-off date, whichever occurred earlier. The OS endpoint is operationalized using a parameterized R function *edb4_get_os()* and more details can be found in the attached pdf documentation.

Table 4. Relevant clinical activities considered to derive last activity date for censoring.

Table / clinical activity considered	Dates considered
Adverse events	Event date
Therapy (cellular, systemic, radiation, surgery)	Start and end dates or declined intervention date, surgery date, assessed resection dates
Palliative care referral	Referral date
Visits	Contact/visit date
Vitals	Assessed date
Labs	Lab date
Biomarkers	Specimen collection date
Patient observation period	Start and end dates

Demographics	Date of most recent contact with provider, date patient was diagnosed with a second primary malignancy
Performance assessments	Documented date, reported date
Secondary diagnoses	Diagnosis date
Progression, histology, lymphovascular invasion, metastatic sites, pancoast tumor, perineural invasion	Assessed date
Stage/TNM	Assessed date
Smoking	Assessed date

